5. PURPOSE OF CLINICAL TRIAL	
Bronchodilator targeting throughout the whole airway tree is important in respiratory disease and more so in COPD where the disease pathology and airflow physiological limitation arises from the small airways. However many drugs do not reach the small airways. Respimat is a novel inhaler platform that has small particles and a slow inhalation allowing deeper lung drug delivery. Small particle ICS and LABA combinations have been shown to improve markers of large and small airways that are also now being translated into meaningful improvements in patients with asthma and COPD [10c].
 
We aim to investigate the effect of tiotropium from different devices on a panel of small (IOS, MBNW, DLCO, FVC) and large airway (FEV1, PEF) responses in patients with mild-moderate COPD. We will compare Tiotropium Handihaler 18 micrograms once daily with Tiotropium Respimat 5 micrograms once daily

6. DESIGN OF CLINICAL TRIAL	Open label. Sequential
7. PATIENT POPULATION IN CLINICAL TRIAL	Mild-Moderate COPD
8. MAXIMUM NUMBER OF PATIENTS TO BE INCLUDED IN CLINICAL TRIAL	N= 44
9. MAIN INCLUSION CRITERIA IN CLINICAL TRIAL	
COPD
 
1) COPD patients with FEV1/FVC <70% predicted.
 
2) Mild (GOLD stage I: FEV1 >80% pred.) to moderate (GOLD stage II: FEV1 50-80% pred.)
 
3) Aged 30 years onwards – there is no upper age limit as we do not want to exclude elderly patients as COPD is primarily a disease in the elderly population.
 
4) Have ongoing symptoms or exercise limitation (determined by CAT score)
 
5) Stable COPD (no chest infection requiring antibiotics and/or oral steroids in the past 2 months).
 
6) Capable of giving informed consent, which includes compliance with the requirements and restrictions listed in the consent form.


10. MAIN EXCLUSION CRITERIA IN CLINICAL TRIAL
	
COPD
 
 
1) We will not recruit subjects who lack the capacity to consent.
 
2) Current or past diagnosis of asthma.
 
3) Patients on concurrent oral bronchodilators (theophylline, PDE4 inhibitors) will not be included.
 
4) Patients on other LAMAs will not be included
 
5) History of any chronic respiratory diseases other than COPD.
 
6) History of another medical condition, which in the opinion of the Unit Physician, contraindicates his/her participation in the study.
 
7) Clinical evidence of heart failure (NYHA class III-IV).
 
8) Unstable respiratory disease in the last four weeks prior to the screening visit (indicated by any change in their maintenance inhaled therapy or who have had a lower respiratory tract infection in the previous four weeks).
 
9) Evidence of a respiratory exacerbation requiring emergency room treatment and/or hospitalisation within four weeks before screening.
 
10) Use of systemic (oral or intravenous) steroids 4 weeks prior to inclusion (injectable depot steroids 6 weeks) or more than 3 periods during the last 12 months.
 
11) Participants with a known or suspected allergy, sensitivity or intolerance to the study drugs (this will be asked directly at the screening visit) or patients with a history of another drug allergy which, in the opinion of the Unit Physician, contraindicates his/her participation in the study.
 
12) Patients with known or suspected cardiac rhythm disorders
 
13) Patients treated with beta-blockers in the week preceding the screening visit and during the study period.
 
14) Females who are pregnant or lactating or are likely to become pregnant during the trial (a urine pregnancy test will be performed. Women of childbearing potential may be included in the study if, in the opinion of the investigator, they are taking adequate contraceptive precautions.
 
15) Patients who have evidence of alcohol or substance abuse.
 
16) Participation in another clinical trial with an investigational drug in the four weeks preceding the screening visit.
 

---	---

11. PROCEDURES FOR SAFETY MONITORING DURING TRIAL	Direct questioning about medical symptoms at the beginning of each study visit (see also 'Safety' section and 'Adverse Events' section below).
12. CRITERIA FOR WITHDRAWAL OF PATIENTS ON SAFETY GROUNDS	Suspected Unexpected Serious Adverse Reaction (SUSAR) The data to be collected on withdrawn subjects and their follow-up is listed under the 'Adverse Events' section (see later).
13. ROUTE(S) OF ADMINISTRATION (use standard terms)	Inhalation
14. MAXIMUM DOSAGE ALLOWED (specify daily or total)	14 days of handihaler tiotropium 18 micrograms once daily (14 x 18 micrograms = 252 micrograms total dose tiotropium via handihaler device) And 14 days of respimat tiotropium 5 micrograms once daily (14 x 5 micrograms = 70 micrograms total dose tiotropium via respimat device) 252 + 70 micrograms = 322 maximum dose tiotropium in study
15. MAXIMUM DURATION OF TREATMENT OF A SUBJECT	28 days
16. ACTIVE COMPARATOR PRODUCT(S)	No
17. ON-GOING TRIALS IN OTHER EU MEMBER STATES	No
18. REGULATORY SUBMISSIONS ON SAFETY GROUNDS	No

[figure not shown]
## 1. BACKGROUND AND RATIONALE (references at end of document)

### Small airways

Patients with asthma and chronic obstructive airways disease (COPD) undergo routine testing of their lung function in the diagnosis, progression, management and, response to treatment of their disease [1]. Standard lung function obtains measurements based on the forced flow of air moving within the airways. Such measurements give a reasonable assessment of disease affecting the large airways, but not an accurate estimate of small airways disease [2]. Small airways are less than 2mm in diameter [Fig. 1]. However, both asthma and COPD have disease that involves not only the large but also the small airways that has important clinical consequences. Indeed, COPD predominantly affects the small airways [3, 3b].

### Silent zone

Figure 1. Small vs. large airways of the lungs. For this reason, the small airways of the lungs are often referred to as the 'silent zone'. This is because airways disease in this zone may not be detected by standard clinical lung function measures, such as spirometry. For example, a recent study showed that small airway function became abnormal after only 10 pack-yrs of smoking, whereas spirometry became abnormal after 20 pack-yrs [4]. Also, lung pathology such as airways inflammation & narrowing and lung tissue destruction may be well-established before patients present with symptoms. This is of particular concern in lung transplant recipients where lung rejection often

starts with small airways disease, which is difficult to monitor [5].

### Clinical healthcare needs

Better clinical assessments of small airways function and physiology are required. Clinicians need information in order to manage small airways disease of the lungs with clinical tests that are non-invasive, specific and do not expose patients to repeat X-Rays (such as CT scans) or are unpleasant and invasive (such as bronchoscopy). Non-invasive lung imaging such as positron emission tomography (PET) and magnetic resonance imaging (MRI) have been used, but give poor image resolution of the small airways compared to larger airways [Fig. 1].

### Sensitive physiological technologies: IOS and MBNW

[figure not shown]

Figure 2. Patient set-up for IOS. We have set-up and validated [6, 7] the impulse oscillometry (IOS) and multi-breath nitrogen washout (MBNW) techniques in our lab. These are non-invasive physiological instruments that give a sensitive assessment of small airways function. They are practical methods of measurement that could be used in everyday clinical practice to routinely measure small airway function because of ease of administration and potentially, production of relatively cheap portable devices [8]. IOS [Fig. 2] uses oscillating pressure-flow signals of moving air within the lungs to determine peripheral lung mechanical parameters [9] which include small airway

resistance and an estimate of lung compliance and air-trapping [Fig. 3], whereas MBNW utilizes the exhalation of nitrogen gas from the airways to determine changes in lung ventilation and derive small airways indices [10]. Patients are seated and gently breathe for a couple of minutes through the machines. Importantly, IOS & MBNW can be comfortably used in children and elderly populations.

[figure not shown]

Figure 3. effect of tiotropim (18 $\mu$ g) on small airway reactance as assessed by IOS. Most recently, we have developed specific technique with IOS to distinguish patients with COPD from asthma [10b].

## Therapeutic target

It is clear that the small airways are an important target in the treatment of asthma, COPD and other respiratory diseases [10c]. Recent clinical trials have used physiologic measures of small airways such as MBNW to assess the intervention of pharmacological treatments such as montelukast [11], inhaled tiotropium [12], inhaled corticosteroid formulated with specific ability to penetrate into the distal lung [13] and also, non-drug interventions such as smoking cessation [14], in the management of patients with asthma and COPD.

[figure not shown]
FEV1 is the standard measurement used to measure drug effects in COPD clinical studies, however it does not reflect small airway resistance and may not provide information about lung compliance. IOS and plethysmography have been shown to have a higher sensitivity than FEV1 for assessing short acting bronchodilator [14b] effects in COPD, and recently these techniques have been shown to sensitively differentiate the effect of tiotropium over salmeterol when FEV1 measurements are similar [14c].

FEV1 is insensitive to small airway changes and to alterations of the lung mechanics. On the contrary, the combined use of IOS, MBNW, and plethysmography besides providing information on the “silent zone” may also reflect changes of lung mechanics. The use of these methods in the same patients is unprecedented and we are confident it will provide valuable physiological and pharmacological data.

## Inhaled drug delivery technologies: drug particle size

Figure 4. Drug particles of 1.5 $\mu$ m in lungs [name] et al AJRCCM 2005. Aerosol drug particle size is the most important determinant of where inhaled drug deposits within the lungs. We have developed and validated an aerosol particle generator system able to produce therapeutic drug aerosols, all of one particle size, for controlled delivery to patients [15]. We have shown that by altering inhaled drug particle size, we can direct inhaled drug to different airway regions in the lungs [16, Fig. 4]. Determining the optimal particle size of inhaled drug therapy may contribute knowledge towards the development of new

inhalers and drugs that require greater selectivity for treating the small airways.

## Small airway function in vitro

We have developed a way to study the pharmacology of small human airways in vitro using precision-cut lung slices and videomicroscopy [16b]. Using this technique we have demonstrated the pharmacological characterization of indacaterol, a novel once daily inhaled 2 adrenoceptor agonist, on small airways in human and rat precision-cut lung slices.

## LAMA'S (tiotropium) in COPD and the Respimat Inhaler

Monotherapy with bronchodilators (LABA or LAMA) are first line therapy in the GOLD guidelines [GOLD]. According to the current GOLD guidelines [GOLD, bronchodilators should be used in preference to LABA and ICS combinations.

**Tiotropium** (Spiriva, Boehringer Ingelheim), a long-acting inhaled anticholinergic bronchodilator, improves lung function, quality of life, and exercise endurance and reduces exacerbations in patients with chronic obstructive pulmonary disease (COPD) [Vogelmeier, C, NEJM 2011; Bateman, Respir Med 2010; Cooper, CB, Chest 2013; Tashkin, DP, N Engl J Med 2008] Tiotropium is approved and marketed as

a dry-powder formulation delivered by means of the HandiHaler inhalation device (at a dose of 18 µg) [Boehringer Ingelheim. Summary of Product Characteristics (SPC): Spiriva 18 microgram inhalation powder, hard capsule. eMC, 2012] and as an aqueous solution delivered by means of the Respimat inhaler (at a dose of 5 µg) in many countries [Summary of Product Characteristics (SPC): Spiriva Respimat 2.5 microgram solution for inhalation. eMC, 2013] Crossover trials of tiotropium Respimat at a dose of 5 µg and HandiHaler at a dose of 18 µg for up to 4 weeks have shown similar efficacy, safety, and pharmacokinetic profiles. [van Noord, JA, Respir Med 2009; Ichinose, M, Respir Med 2010]. Cross-study comparisons have suggested the potential superiority of tiotropium Respimat in terms of COPD exacerbations, as compared with HandiHaler [Bateman, Respir Med 2010; Tashkin, DP, N Engl J Med 2008]. Recently, Tiotropium Respimat at a dose of 5 µg or 2.5 µg had a safety profile and exacerbation efficacy similar to those of Tiotropium HandiHaler at a dose of 18 µg in patients with COPD \*Wise, NEJM 2013].

**Respimat** Soft MistTM Inhaler (SMI) is a novel inhaler delivering a unique slow-moving Soft MistTM that allows gentle inhalation – making it easy to inhale. Importantly it has drug particles that are ~ 2microns [16c] that allow an increase in the total lung deposition of drug (~52%) [16d] and also the potential for penetration to treat the small and large airways in patients with COPD; that is targeting the whole airway tree.

## **2. QUESTIONS THIS STUDY WILL ANSWER**

PHASE 1: Effect of Inhaler Training with Handihaler on airway function and symptoms

If we train patients with the Handihaler properly can we

- improve (i) lung function (large and small airway)?
- improve(ii) clinical symptoms (determined by CAT score)?

Mild-moderate COPD [GOLD], established (>1 month) already on HandiHaler- Tiotropium 18 mcg once daily but have ongoing symptoms or exercise limitation (determined by CAT score) to be eligible to enter. So their clinical state may be due to 'real-life' poor inhaler technique (which will be assessed by the research observer). Patients receiving Handihaler who have not been trained for over 3 months on its use will be recruited.

We will train patients in the optimal use of the Handihaler.

So if we train patients with the Handihaler properly can we improve (i) lung function (large and small airway) and (ii) clinical symptoms (determined by CAT score).

Data comparison: Data from Visit 1 will be compared to the Screening Visit data.

PHASE 2: Is the device important in treating the small airways

- Does changing the device from a DPI-Handihaler (in a trained patient) to a SMI-Respimat give an added advantage to the patient? (keeping the dose of the drug equivalent from each device – that is Tio 18mcg HH = Tio 5mcg Resp).
- That is – is there an added advantage with the device that is observed with a change (improvement) in (i) lung function (large and small airway) and (ii) clinical symptoms (determined by CAT score).

- Do the properties of the Respimat device with deeper lung deposition (slow velocity and small particles) can improve small airway measures (and indeed large airway measures) that might also be related to an improvement in symptoms.

Data comparison: Data from Visit 2 will be compared to the Visit 1 data.

### **3 . RESEARCH AIM & HYPOTHESIS**

We aim to investigate the effect of tiotropium from different devices on a panel of small (IOS, MBNW, DLCO, FVC) and large airway (FEV1, PEF) responses in patients with mild-moderate COPD. We will compare Tiotropium Handihaler 18 micrograms once daily with Tiotropium Respimat 5 micrograms once daily.

We will identify a COPD cohort with ongoing symptoms or exercise limitation on HandiHaler, as proposed. The science behind this is why are people still limited (even if partially as determined using the CAT score) and could it be that relatively we need more distal airway targeting (this doesn't necessarily mean acinar/alveolar beyond the terminal bronchioles, but just a little bit more going deeper into the distal conducting airway) that can be achieved with Respimat.

### **4. STUDY DESIGN:** (also see **study treatment dosing flowchart below**)

**Target population: N=44 mild COPD patients.**

Open (as patients can identify inhaler device), Sequential, 3 visits (including screening visit).

Patients on concurrent oral bronchodilators (theophylline, PDE4 inhibitors) will not be included. Patients on concurrent LABAs will be allowed.

**N=44 Patients:** Mild-moderate COPD [GOLD], established (>1 month) already on HandiHaler- Tiotropium 18 mcg once daily **but have ongoing symptoms or exercise limitation (determined by CAT score)**

There will be three phases.

- **Phase 0** (Screening visit)  
Patients receiving Handihaler who have not been trained (real-life use) for over 3 months on its use
- **Phase 1**  
Patients will be trained in their use of Handihaler-Tiotropium and asked to take 18 mcg once daily for 14 days to see if their (i) airway lung function and or (ii) clinical symptoms improve AND THEN
- **Phase 2**  
Patients will be switched to trained Respimat Tiotropium 5 mcg once daily for 14 days to see if their (i) airway lung function and or (ii) clinical symptoms improve.

#### **WHAT HAPPENS AT EACH VISIT?**

##### **(i) Phase 0 - SCREENING VISIT: (DAY 0)**

- IDENTIFY : Mild-moderate COPD [G.O.L.D], established (>1 month) already on HandiHaler- Tiotropium 18 mcg once daily but have ongoing symptoms or exercise limitation (determined by CAT score) to be eligible to enter
- Patient to avoid short acting SABA and SAMA and LABA on day of visit

- 9am Baseline: Lung physiology measurements undertaken in this order; IOS, MBNW, Spirometry (FVC) /Body plethysmography (DLCO).
- Patient asked to demonstrate how they use Handihaler with a demonstration device. Research observer notes how patient takes Handihaler-Tiotropium to assess good or poor inhalation technique /errors.
- Patient receives training in how to use Handihaler correctly until observer satisfied.
- 10am Patient takes Handihaler-Tiotropium 18 mcg od in Lab. Research observer notes how patient takes Handihaler-Tiotropium.
- 3hours post dosing: Lung physiology measurements undertaken in this order; IOS, MBNW, Spirometry (FVC) /Body plethysmography (DLCO).

Tests:

- Small (IOS, MBNW, DLCO, FVC) airways (these will be done on physiology machines of [name])
- Large (FEV1, PEF) airways (these will be done on physiology machines of [name])
- CAT score

**AIM OF THIS PHASE (0) OF STUDY:** Here we want to see that if patients have ongoing symptoms but are on Handihaler-Tiotropium what is happening PRIOR to proper inhaler technique training – that is their ‘real-life’ use of the inhaler - to their lung function (large and small airways) and also symptoms or exercise limitation (determined by CAT score) will already be recorded as entry criteria

- Patient will be asked to take Handihaler-Tiotropium 18 mcg od at 10am every day for 14 days

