### **Inclusion Criteria**

- 1) Patients with FEV1/FVC <70% predicted.
- 2) Mild (GOLD stage I: FEV1 >80% pred.) to moderate (GOLD stage II: FEV1 50-80% pred.)
- 3) Aged 30 years onwards – there is no upper age limit as we do not want to exclude elderly patients as COPD is primarily a disease in the elderly population.
- 4) Have ongoing symptoms or exercise limitation (determined by CAT score)

- 5) Stable COPD (no chest infection requiring antibiotics and/or oral steroids in the past 2 months).
- 6) Capable of giving informed consent, which includes compliance with the requirements and restrictions listed in the consent form.

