**The primary endpoint is the Impulse oscillometry measure of IOS R5-R20.**

**Each subject will act as their own control and assuming the treatment effect (ie the difference R5-R20 between baseline and 14 days) to be 0.03kPa(L/s) with an SD of 0.05, then 44 subjects will be required to achieve the treatment effect at 1% significance and 90% power.**

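### The Screening CAT appears to serve both as entry criterion and as the Phase 1 baseline, so part of any CAT fall by Visit 1 may be regression to the mean

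*Protocol*

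**What the plan says.** **Selection.** Inclusion criterion 4 (protocol section 5) reads "Have ongoing symptoms or exercise limitation (determined by CAT score"). Section 4(i), under the Day 0 heading, repeats that patients need "ongoing symptoms or exercise limitation (determined by CAT score) to be eligible to enter". Section 13 withdraws patients who fail eligibility, so the criterion is enforced. No numerical CAT limit is given.

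**Baseline.** Section 4(i) describes its aim as recording the state before inhaler training, and adds that "symptoms or exercise limitation (determined by CAT score) will already be recorded as entry criteria". The same section also lists CAT among the Day 0 tests.

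**Comparison.** Section 2 asks whether training can "improve(ii) clinical symptoms (determined by CAT score"). It answers this with "Data from Visit 1 will be compared to the Screening Visit data".

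**Design and analysis.** Section 4 describes the study as "Open (as patients can identify inhaler device), Sequential, 3 visits (including screening visit"). Section 10 says "Each subject will act as their own control". CAT is listed there as a secondary endpoint. The SAP names t-tests or Mann-Whitney tests, and mixed models with adjustment for baseline covariates. Neither document mentions regression to the mean.

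**The concern.** A score that admits a patient by being high enough carries, on average, some upward chance error. When the questionnaire is repeated, that error is not reproduced and the mean drifts down. If the admitting score is also the starting point for measuring change, the drift is counted as improvement.

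Phase 1 has no untrained group to show how far CAT would have moved anyway. Baseline adjustment does not fill the gap. Regressing the change on baseline and evaluating the fit at the sample's own mean baseline returns the same mean change. Correcting it would take an untrained group, or outside knowledge of the unselected mean and the repeatability.

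At stake is one of the two questions posed for Phase 1: whether training relieves symptoms. The bias favours the answer yes.

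**Working it through.** **1. The plan's own figure.** The only sample-size figure concerns R5-R20: effect 0.03, SD 0.05, 1% significance, 90% power. Taking 0.05 as the SD of the within-patient difference and a two-sided test, n = (0.05 × (2.576 + 1.282) / 0.03)² = 41.3, so 42. The exact t calculation gives 45. The stated 44 lies within two patients of either. It says nothing about CAT, and only n = 44 carries over.

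**2. Inputs for CAT.** From the documents: n = 44, one group, change = Visit 1 minus Screening. Not in the documents, hence assumed: SD 7, unselected (source) mean 13-15, test-retest ICC 0.7-0.85, cut-offs 1, 5 and 10, and a two-sided 5% paired t-test (the SAP sets no level for CAT).

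**3. Formula.** Assume normal scores, stable true CAT and no training effect. For patients scoring at or above cut-off c:

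expected fall = SD × (1 − ICC) × φ(z) / (1 − Φ(z)), with z = (c − mean) / SD.

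This is above zero whenever the cut-off excludes someone and ICC is below 1.

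**4. One case in full.** Cut-off 10, mean 13, ICC 0.8:
- z = (10 − 13)/7 = −0.429; φ(z) = 0.364; 1 − Φ(z) = 0.666; ratio 0.547.
- Expected fall = 7 × 0.2 × 0.547 = 0.77 points.
- The simulated SD of the change is about 4.3, so its standard error is 4.3/√44 = 0.65, and the fall is about 1.2 standard errors.
- In simulation, about 21% of such trials declare CAT improved, against 2.5%.

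**5. Across the assumed range** (SD 7, mean 13-15, ICC 0.7-0.85; simulated trials of 44 patients, counting only rejections in favour of improvement):

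| Cut-off | Source patients excluded | Spurious fall (points) | False improvement (nominal 2.5%) |
|---|---|---|---|
| 1 | 2-4% | 0.06-0.2 | about 3-4% |
| 5 | 8-13% | 0.16-0.5 | about 5-9% |
| 10 | 24-33% | about 0.4-1.2 | about 10-30% |

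Higher cut-offs or lower source means give more. Cut-off 15 with ICC 0.7 gives 2.08 points and about 75% at mean 13, and 2.73 points and about 94% at mean 10.

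**6. If the 1% level were applied to CAT.** With cut-off 10 (set at 9.5 to allow for whole-number scores) and ICC 0.8, rejections in either direction run at 2.9% for mean 15 and 8.8% for mean 12, against a nominal 1%.

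**The case against.** **One reading or two?** Section 4(i) lists CAT among the Day 0 tests, apart from the eligibility bullet, and says symptoms will already have been recorded. That could mean an entry CAT followed by a fresh Day 0 CAT, which is what one would want. This reading stays open. It is the less natural one, because the eligibility check sits under the Day 0 heading and nothing separates a qualifying score from a baseline score. If two readings are intended, the protocol still has to say which is the baseline.

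**The bar may be low.** Section 3 speaks of patients who may be only partly limited by CAT, which fits a low cut-off. In that case hardly anyone is excluded and the bias is close to nil. This stands, and it rules out presenting the large figures as the expected size.

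**Stronger claims a reader might infer.**
- That most trials run this way would falsely show a CAT benefit. Rates of 75% or more need a cut-off of 15 and poor repeatability, neither of which is in the documents.
- That the primary endpoint is biased in the same way. R5-R20 is not the selection variable and is touched only through any correlation with CAT.
- That the Visit 2 versus Visit 1 CAT change is entirely free of the problem. It is largely spared, but if chance deviations persist for weeks, some drift can continue into Phase 2.

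**Limited gain.** Even with a clean baseline, Phase 1 remains open-label and uncontrolled. That is true; the repair removes one known bias and does not make the comparison causal.

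**Conclusion.** The point holds in qualified form. As most naturally read, the Screening CAT both selects patients and is the Phase 1 starting value. Provided the entry limit excludes some patients and CAT is less than perfectly repeatable, a fall by Visit 1 is expected without any training effect, and the planned analysis cannot separate the two.

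The direction follows from the design; the size does not. On the assumptions above it runs from negligible at a cut-off of 1 to about a point at a cut-off of 10, and further if the limit is stricter. Because the cut-off is unstated, a reader cannot tell which case applies. The consequence is confined mainly to a secondary endpoint in Phase 1, so this is a worthwhile improvement and not a threat to the main result.

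**What to change.** 1. State the CAT entry cut-off in protocol sections 4(i) and 5.
2. Specify that the qualifying CAT is recorded after consent and before Day 0 testing. Specify too that a separate Day 0 CAT, taken before HandiHaler training and never used to exclude anyone, is the sole baseline for the Visit 1 comparison.
3. If a separate reading is not feasible, say in the SAP that the Phase 1 CAT change is descriptive, includes regression to the mean, and will not be taken as evidence that training improves symptoms.

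**Cost.** Options 1 and 2 need a few sentences and one extra short questionnaire per patient. The enrolment appointment in section 12 is a possible slot, but no assessment is described there. Consent would have to come first, and an added contact might be needed. The apparent CAT gain will probably be smaller. If the two readings are close together their errors will be correlated, so the bias is only partly removed; the report should say so. Option 3 costs one sentence.

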## **8. DRUG DOSING**

The study drugs, Handihaler tiotropium 18 micrograms and Respimat tiotropium 5 micrograms and the placebo, for training purposes, will be supplied by Boehringer Ingelheim (Germany) to the Pharmacy of the Royal Brompton Hospital where it will be stored until required. Labels will be assigned to study medication and placebo in accordance to the protocol and ICH GCP by the Pharmacy of the Royal Brompton Hospital – as final packaged medication for each patient. The labels on the packages and unit medication will specify all necessary information for a correct identification of the medication boxes and individual medication units. The Pharmacy of the Royal Brompton Hospital will dispense the study drugs to the patients. All study medication accountability will be performed at the Royal Brompton Hospital by members of the study team and returned/unused medication will be destroyed by the Royal Brompton Hospital Pharmacy at study closure.

We will give 14 days duration of treatment in order to achieve steady state dosing of Tiotropium drug.

- The first dose will be given in the Hospital but subsequent doses will be taken at home.
- Dosing of the drug will be undertaken at the same time each day (ideally 9am)
- We will undertake measurements 3 hours post dosing (applies only to the dose given in the department). The reason we have used 3 hours is to achieve the maximal response pharmacologically with Tiotropium in order to elicit differences within Phase 1 of the study (device training ) and Phase 2 (device effects) in Study Group 1.
- We will use Handihaler tiotropium 18 micrograms daily which is licensed for use in COPD.
- We will use Respimat tiotropium 5 micrograms daily which is licensed for use in COPD.

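### Phase 1 reads the Visit 1 minus Screening change as the effect of HandiHaler training, but a daily dosing instruction and trial-dispensed drug start on the same day and prior use is not recorded

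*Protocol*

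**What the plan says.** Protocol section 2 poses the Phase 1 question as one about training: "So if we train patients with the Handihaler properly can we improve (i) lung function (large and small airway) and (ii) clinical symptoms". The contrast that answers it is also given there: "Data from Visit 1 will be compared to the Screening Visit data".

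Section 4 describes an open, sequential study with three visits and a single group. Patients enter more than one month into HandiHaler treatment and still limited: "already on HandiHaler- Tiotropium 18 mcg once daily but have ongoing symptoms or exercise limitation (determined by CAT score) to be eligible to enter". The stated aim of the Screening phase is to see "what is happening PRIOR to proper inhaler technique training", which the protocol calls real-life use.

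On Day 0 (section 4(i)) the order is: 9am lung physiology, a demonstration of technique scored by an observer, training until the observer is satisfied, an observed 10am dose, and physiology three hours later. The patient then goes home with this instruction: "Patient will be asked to take Handihaler-Tiotropium 18 mcg od at 10am every day for 14 days".

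Section 8 adds that the hospital pharmacy dispenses the study drugs, that doses after the first are taken at home, and that "All study medication accountability will be performed at the Royal Brompton Hospital by members of the study team". Section 8 gives 9am as the ideal dosing time, whereas sections 4(i) and 4(ii) give 10am.

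The SAP names t-tests or Mann-Whitney tests and linear mixed models, adjusted for baseline variables that it does not list.

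**The concern.** At least three things start on Day 0: correct technique, an explicit instruction to dose every day at a set time, and trial-supplied drug that will be counted. Any of them can change how much drug reaches the airway between Screening and Visit 1. Section 2 credits the whole change to the first.

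The patients are chosen because they still have symptoms on HandiHaler. The protocol suggests poor technique as the reason, but missed doses would be an equally natural one. A patient whose technique was already perfect, and who simply began taking every dose, would also improve. Checking technique at entry or at Visit 1 would therefore not settle the matter.

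At stake is the meaning of one of the study's two stated questions. A positive R5-R20 or CAT result in Phase 1 would be reported as a benefit of training when the contrast cannot say so, and data not collected before the Day 0 instruction cannot be reliably reconstructed afterwards.

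**Working it through.** **1. Which measurements can carry the Phase 1 contrast.** The three-hour reading at Screening comes after training. The three-hour reading at Visit 1 comes after the first Respimat dose. Only the two 9am readings compare HandiHaler before training with HandiHaler after it.

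**2. What is known about drug exposure before each 9am reading.**

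| | Before Screening, 9am | Before Visit 1, 9am |
|---|---|---|
| Technique | observed and scored | trained on Day 0 |
| Supply | patient's existing treatment | trial pharmacy, under accountability |
| Doses taken | not recorded | accountability may show this |
| Usual dosing time | not recorded | 10am as instructed (section 8: ideally 9am) |
| Time since last tiotropium dose | not recorded | about 23 h if dosed at 10am the day before |

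The instruction on drugs to avoid on the day of a visit names SABA, SAMA and LABA. The planned 10am clinic dose suggests that tiotropium is not meant to be taken earlier that morning, but the text does not say so. Accountability covers study drug only, so it has no pre-study counterpart. An adherence variable that was never collected cannot be among the SAP's baseline variables.

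**3. The plan's own figure.** Inputs from section 10 and the SAP: effect 0.03 kPa/(L/s), SD 0.05 (taken as the SD of the within-patient change), 1% significance, 90% power.

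n = [SD × (z₀.₉₉₅ + z₀.₉₀) / effect]² = [0.05 × (2.576 + 1.282) / 0.03]² = 41.3, so 42.

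The exact noncentral t gives power 89.4% at n=44 and 90.2% at n=45. The planned 44 is consistent with a two-sided 1% paired test and is not in question. One-sided 1% would give 37.

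**4. What a non-training shift would do.** Take improvement as positive and let the true training effect be zero. At n=44 the standard error is 0.05/√44 = 0.00754 and the critical t on 43 df is 2.695. The smallest significant mean change is 2.695 × 0.00754 = 0.0203. For an assumed shift b from other causes, the noncentrality is b/0.00754, and the chance of a significant improvement is:

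| Assumed shift b | Share of planned 0.03 | Chance of a significant improvement |
|---|---|---|
| 0 | 0% | 0.5% |
| 0.003 | 10% | 1.4% |
| 0.005 | 17% | 2.6% |
| 0.010 | 33% | 9.7% |
| 0.015 | 50% | 25.4% |

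The shifts are assumptions; nothing in the documents fixes them. More patients would not remove such a shift, and would make a given shift more likely to reach significance.

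**The case against.** **The protocol already describes a package.** Section 4 says that in Phase 1 patients are trained and asked to take 18 mcg once daily for 14 days, and it calls the comparator real-life use, which can include real-life adherence. On that reading the remaining fault is that section 2 shortens the package to training. This stands in part: relabelling is much of the remedy. It does not cover the missing record of prior use.

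**A reader might infer that daily dosing becomes supervised or enforced.** The documents do not support that. One Day 0 dose is observed, section 8 puts later doses at home, and the patient is only asked to take them. Nor do they show that dosing time changes: prior dosing time is unrecorded, so it may change for an unknown share of patients. Drug, device, dose and frequency are the same before and after Day 0, and a change of supplier is not by itself a cause of improvement.

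**A reader might also infer that a positive result would probably be all adherence.** That needs a large full drug effect. If the full effect on R5-R20 were 0.06 to 0.10, proportional to doses taken, with near-full use on study, 80% prior adherence would shift the mean by 0.012 to 0.020, with a 15% to 49% chance of significance. No such effect is in the documents. With a full effect of 0.03, the only size they give, prior adherence of 90%, 80% and 70% gives shifts of 0.003, 0.006 and 0.009, and chances of 1.4%, 3.5% and 7.7%.

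**Visibility and scope.** The dosing flow-chart is not shown and the case report form is not among the documents, so prior use might be captured there. The section 3 aim is the device comparison, which Phase 2 addresses. Both points are fair and limit the finding to the readable procedures and to Phase 1.

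**Conclusion.** The concern holds in a limited form. Phase 1 is an uncontrolled before-after contrast in which training coincides with an instruction to dose daily and with trial-dispensed, counted drug. The readable procedures do not record the prior use needed to tell these apart, so section 2 claims more than the contrast can carry.

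The size is unknown. On assumed non-training shifts of 0.003 to 0.015, the chance of a significant improvement with no training effect runs from about 1% to 25%, against 0.5% with no shift. This rests on n=44, SD 0.05 for the within-patient change, a two-sided 1% paired t-test and the assumed shifts. A difference in time since last dose could act in either direction, so it could also hide a real training effect.

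The sample size is not in error. Pre-Screening adherence does not bear on Phase 2, whose Visit 1 and Visit 2 readings both follow trial dosing.

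**What to change.** 1. **Record prior use at Screening, before training and before the dosing instruction:** date and time of the last HandiHaler dose, usual dosing time, doses missed in the previous 14 days, and last refill. At Visit 1, record last-dose time and missed doses, with the capsule count from accountability.
2. **Add a supportive analysis to the SAP:** report the Phase 1 R5-R20 contrast by, or adjusted for, prior adherence and time since last dose. Keep it descriptive. It should not decide whether a training claim may be made: if half the patients reported full prior use (n=22), power for 0.03 would be about 51%, and regression to the mean and trial-participation effects would remain in that subset.
3. **Reword section 2:** describe the Phase 1 estimate as the before-after change with training plus instructed daily dosing under trial conditions, not as the effect of training alone.
4. **Reconcile the dosing times** in sections 4(i) and 4(ii) (10am) with section 8 (ideally 9am).

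The cost is a few record fields and some wording, with no new visit or test. The drawbacks are that self-reported adherence is imperfect and that the Phase 1 conclusion becomes weaker.
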